## **4.1 Interim Analysis**

No interim analyses are planned for this study.

## **4.2 Analysis Populations**

Inclusion and exclusion from each analysis set will be decided at the Data Review Meeting (BDRM) prior to database lock. Further exclusions may be made from PK/PD/Immunogenicity sets based on the concentrations.

### Enrolled

All subjects who sign the ICF.

### Safety Population

The safety population will consist of all subjects who receive at least 1 dose of the study drug.

### PK Population

The PK population will consist of all subjects who have sufficient plasma samples to enable the calculation of PK parameters of at least Area Under the Curve (AUC) for at least one period.

### PD Population

The PD population will consist of all subjects who have sufficient plasma samples which will enable the evaluation of the PD effects, i.e. who have at least one change from baseline value available of either plasma Cp or copper levels (total Cu, Cp, CpC and NCC).

## **4.3 Subject Disposition**

All subjects will be included in the summary of subject disposition. This will present the overall number of subjects screened. It will also present by cohort and overall the frequency and percentage of subjects randomized, treated, and who completed or discontinued from the study, along with the reason for discontinuation.

Furthermore, the number and percentage of subjects in each study population will be tabulated. Discontinued subjects will be listed. Subject assignment to study populations will be listed. Screen Failures will not be listed or included in summary tables.

## **4.4 Demographic Characteristics**

Individual subject demographics (including age, sex, race, ethnicity) and body measurement data (height, body weight and body mass index) at screening will be listed and summarized for each cohort and overall for the safety population. If

the remaining populations are different from the safety population by more than 5%, separate demographic tables will be produced.

For the Japanese cohort, information about the Japanese criteria information (descent, place of birth and residence) will be listed.

Height will be measured in centimeters and weight in kilograms. Body mass index will be given in kg/m^2.

#### **4.5 Baseline and Other Safety Characteristics**

Data collected from serology (HIV and Hep) tests, serum pregnancy test, alcohol breath test and urine drug screen will be listed by subject.

#### **4.6 Inclusion and Exclusion Criteria**

The inclusion and exclusion criteria will be listed together with the overall eligibility for each subject.

#### **4.7 Protocol Deviations**

The final review of protocol deviations will be performed at the BDRM prior to database lock. The protocol deviations will be listed.

#### **4.8 Medical History**

Medical history data will be coded using the Medical Dictionary for Regulatory Activities (MedDRA) dictionary Version 21.1 (or higher) and listed individually. Surgical histories will be listed separately.

#### **4.9 Study Drug Administration**

Study drug administration data will be listed individually.

#### **4.10 Prior and Concomitant Medications**

Prior and concomitant medication will be coded using the World Health Organization drug dictionary (WHO-DD) version June 1, 2018 or higher.

Prior and concomitant non-drug therapies will be coded using the MedDRA version 21.1 or higher.

Prior medications/therapies are defined as those for which the end date and time is prior to the date and time of first study drug administration.

Concomitant medications/therapies are defined as those with start date and time on or after the date and time of first study drug administration, or those with start date and time prior to the first study drug administration but with end date and time on or after the date and time of first study drug administration. Concomitant medications will further be assigned to the Period in which they commence. Concomitant medications of Period 1 are defined as those with start date and time on or after the date and time of study drug administration in Period 1 and before study drug administration in Period 2. Concomitant medications of Period 2 are defined as those with start date and time on or after the date and time of study drug administration in Period 2.

If medication/therapy dates are incomplete and it is not clear whether the medication/therapy was concomitant, it will be assumed to be concomitant.

All prior and concomitant medications/therapies will be listed by subject using reported name, ATC Term and WHO-DD Preferred Name, indication, dose, dose unit, frequency, route of administration, start date and end date or 'ongoing' flag and duration of use. Concomitant medications will be flagged.

The number and percentage of subjects with concomitant medication/therapy will be summarised overall and by WHO-DD Preferred Name and ATC Term using the safety population.

Non-pharmacologic therapies and procedures and prophylactic antibiotic treatment will be listed.

## **4.11 Safety Analysis**

All safety analyses will be performed on the Safety Population.

Safety analyses will include an analysis of all AEs, ECGs, clinical laboratory data, physical examinations, and vital sign measurements using descriptive statistics.

No inferential statistical analyses are planned on the safety parameters of this study.

### **4.11.1 Adverse Events**

A Treatment Emergent Adverse Event (TEAE) is any adverse event that commences after the start of administration of study drug. TEAEs will further be classified by the Period in which they commenced. A TEAE will be classified as Period 1 if the AE start date/time is on or after the date and time of drug administration in Period 1, and Period 2 if the AE start date/time is on or after the date and time of drug administration in Period 2.

The incidence of TEAEs (after dosing) will be summarized using the safety population. The MedDRA dictionary Version 21.1 (or higher) will be used to classify all AEs reported during the study by System Organ Class (SOC) and Preferred Term. A summary of TEAEs including the incidence of subjects who experienced TEAEs (number and percentage of subjects) and incidence of TEAEs (number of events) will be presented for each cohort and overall, by severity and by relationship to study drug.

TEAEs and serious TEAEs will be summarized by SOC and Preferred Term for each cohort and overall, and by relationship to study drug.

Subjects having multiple AEs within a category (e.g., overall, SOC and Preferred Term) will be counted once in that category. For severity tables, a subject's most severe event within a category will be counted. For relationship tables, a subject's event with greatest relationship to study drug within a category will be counted.

All adverse events will be listed. Serious TEAEs and AEs resulting in withdrawal from the study will be listed.

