#### **Events Meeting the AE Definition**

- Any abnormal laboratory test results (hematology, clinical chemistry, or urinalysis) or other safety assessments
  (eg, ECG, radiological scans, vital signs measurements), including those that worsen from baseline, considered
  clinically significant in the medical and scientific judgment of the investigator (ie, not related to progression of
  underlying disease).
- Exacerbation of a chronic or intermittent pre-existing condition including either an increase in frequency and/or intensity of the condition.
- New conditions detected or diagnosed after study drug administration even though it may have been present before the start of the study.
- Signs, symptoms, or the clinical sequelae of a suspected drug-drug interaction.
- Signs, symptoms, or the clinical sequelae of a suspected overdose of either study drug or a concomitant medication. Overdose per se will not be reported as an AE/SAE unless it is an intentional overdose taken with possible suicidal/self-harming intent. Such overdoses should be reported regardless of sequelae.

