### **Assessment of Event Severity**

The Investigator will make an assessment of intensity for each AE and SAE reported during the study and assign it to 1 of the following categories from CTCAE v5.0, published 27 Nov 2017. Each CTCAE term is a Lowest Level Term per MedDRA. Each Lowest Level Term will be coded to a MedDRA Preferred Term:

- 1. Grade 1: Mild (asymptomatic or mild symptoms; clinical or diagnostic observations only; intervention not indicated)
- 2. Grade 2: Moderate (minimal, local or noninvasive intervention indicated; limiting age-appropriate instrumental activities of daily living [ADL])
- 3. Grade 3: Severe (severe or medically significant, but not immediately life-threatening; hospitalization or prolongation of hospitalization indicated; disabling; limiting self-care ADL)
- 4. Grade 4: Life-threatening consequences; urgent intervention indicated
- 5. Grade 5: Death related to AE

Any change in the severity of an AE should be documented based on specific guidelines in the CRF Completion Guidelines.

Severity and seriousness must be differentiated: severity describes the intensity of an AE, while the term seriousness refers to an AE that has met specific criteria for an SAE as described above.

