#### Follow-up of Adverse Events and Serious Adverse Events

• The Investigator is obligated to perform or arrange for the conduct of supplemental measurements and/or evaluations as medically indicated or as requested by the Sponsor or designee to elucidate the nature and/or causality of the AE or SAE as fully as possible. This may include additional laboratory tests or investigations, histopathological examinations, or consultation with other health care professionals.

- If a subject dies during participation in the study or during a recognized follow-up period, the Investigator will provide the Sponsor or designee with a copy of any postmortem findings including histopathology.
- New or updated information will be recorded in the originally completed CRF.
- The Investigator will submit any updated SAE data to the Sponsor or designee within 24 hours of receipt of the updated information.

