### 3.2 Duration of Study

The planned study duration for each subject is approximately 56 days; up to 27 days for screening and approximately 29 days for dosing and follow-up.

\* In Dosing Period 1 and Dosing Period 2, subjects will receive 15 mg and 60 mg of ALXN1840, respectively. Subjects will be readmitted to the CRU for Dosing Period 2 dosing after a minimum of 14 days after the 15 mg dose.

\*\* EOS visit to take place 14 days (+2 days) following 60 mg dose of study drug.  
Abbreviations: CRU = Clinical Research Unit; EOS = end of study, PD = pharmacodynamics;  
PK = pharmacokinetics.

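### SAP 4.11.1 assigns adverse events to a dose by start date only, gives Period 1 no end, and has no rule for an event that worsens after the 60 mg dose

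*SAP*

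**What the plan says.** SAP 4.11.1 defines treatment emergence by onset: "A Treatment Emergent Adverse Event (TEAE) is any adverse event that commences after the start of administration of study drug". It adds that "TEAEs will further be classified by the Period in which they commenced". An event belongs to "Period 1 if the AE start date/time is on or after the date and time of drug administration in Period 1", and to Period 2 on the same wording with the Period 2 dose. No end is given for Period 1.

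Period and dose coincide for everyone (SAP 3.2): "In Dosing Period 1 and Dosing Period 2, subjects will receive 15 mg and 60 mg of ALXN1840, respectively".

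The neighbouring rule for concomitant medications (SAP 4.10) is bounded. Period 1 medications start "on or after the date and time of study drug administration in Period 1 and before study drug administration in Period 2".

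On worsening, protocol 10.3.4 says: "Any change in the severity of an AE should be documented based on specific guidelines in the CRF Completion Guidelines". Its follow-up instructions add: "New or updated information will be recorded in the originally completed CRF". Neither document says which start date, grade or period an event carries once its severity has changed.

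On layout, SAP 4.11.1 specifies the TEAE summaries per cohort and for all subjects together, and does not mention period there. SAP section 4 sets a general layout by cohort and period unless a section states otherwise.

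**The concern.** The sequence is fixed, with the lower dose first and four times that dose about 14 days later. A complaint that is mild after 15 mg, persists, and worsens after 60 mg is one plain way for a dose-related effect to show. A rule based only on when the event began sends it to the 15 mg period, whatever happened after the second dose. If by-period tables are then used to describe tolerability at each dose, the 60 mg column can look cleaner than the data are. The open-ended Period 1 definition is a separate flaw in the same sentence: read literally, it also counts events that start after 60 mg under 15 mg.

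**Working it through.** There is no plan figure to reproduce, because the point is a classification rule. The check applies the written rules to simple cases.

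**Inputs.** Onset-only rule and period definitions: SAP 4.11.1. Bounded comparison rule: SAP 4.10. Period-to-dose link: SAP 3.2. Recording of severity changes: protocol 10.3.4. Cohort sizes: 12 enrolled, at least 10 completing (SAP 3.3).

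**Step 1: the Period 1 window.** Put the 15 mg dose at day 0 and the 60 mg dose at day 14. Take one event starting on day 5 and another on day 15.

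| Rule | Period 1 | Period 2 |
|---|---|---|
| SAP 4.11.1, read literally | day 5 and day 15 | day 15 |
| Same events under the SAP 4.10 wording | day 5 | day 15 |

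The day 15 event meets both definitions in SAP 4.11.1. The sentence before them, on the period of commencement, suggests that one period was meant, but the definitions do not deliver that.

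**Step 2: an event that worsens.** Take one subject with a Grade 1 event starting on day 5 that reaches Grade 3 on day 15. Use the intended reading, with Period 1 ending at the second dose. Three recording conventions are compatible with the documents:

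| Convention | Period 1 (15 mg) | Period 2 (60 mg) |
|---|---|---|
| (a) one record, worst grade | Grade 3 | none |
| (b) new record at worsening | Grade 1 | Grade 3 |
| (c) one record, onset grade | Grade 1 | none |

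The pattern is the same for Grade 1 to 2 and for Grade 2 to 3. Only (b) shows the worsening at the dose it followed. Under (a) and (c) the 60 mg column loses it, and no convention wrongly adds an event to 60 mg.

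The SAP severity rule does not choose between these. It picks the worst of several events in a category and does not say what grade one changing event carries.

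**Step 3: which tables are affected.**
- TEAE tables by cohort and overall: period attribution makes no difference. Convention (c) would understate the grade there too, but that is a matter of grading, not of period.
- TEAE tables by period, which follow from the general layout in SAP section 4: affected.
- Laboratory shift tables (SAP 4.11.2): these use the worst post-dose grade within each period, so laboratory worsening after 60 mg would appear in Period 2, against a Period 2 baseline.

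**Step 4: weight of one subject.**
- Cohort of 12: 1/12 = 8.3 percentage points.
- Cohort of 10: 1/10 = 10.0 points.
- All 24: 1/24 = 4.2 points.

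Relative to (b) in a cohort of 12, convention (a) adds 8.3 points to the Period 1 rate at the higher grade and takes 8.3 points from Period 2. Convention (c) takes 8.3 points from Period 2 only.

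**The case against.** The case against runs as follows. The outcome depends on CRF guidelines that are not in the documents. If sites open a new record when severity changes, the onset rule puts the worsening in Period 2 correctly. The TEAE tables that SAP 4.11.1 names are by cohort and overall, where period does not matter. The secondary objective concerns safety in Japanese and non-Japanese subjects; it is not framed as a comparison of doses, and no inferential safety analysis is planned. All adverse events are listed, and with about 24 subjects a reader can find a worsening event. Protocol 6.7 also narrows the field: a related TEAE of Grade 3 or higher bars the 60 mg dose, as does a related Grade 1 or 2 TEAE that the Safety Review Committee regards as a safety concern.

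Most of this stands and limits the point, but it does not remove it. The general layout rule calls for presentation by period and SAP 4.11.1 states no exception. Classifying TEAEs by period would have little purpose if they were not reported that way. Unrelated events, and related Grade 1 or 2 events not judged a concern, can still be ongoing at the second dose. The laboratory shift tables do not capture symptoms, which were the commonest adverse events in the two earlier healthy-subject studies (protocol 2.2).

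Two stronger readings are tempting but not supported:
- A reader might infer that a condition present before the first dose and worsening afterwards is lost as a TEAE. Protocol 8.3.1 treats occurrences before the first dose as medical history, and protocol 10.3.1 lists as an adverse event "Exacerbation of a chronic or intermittent pre-existing condition including either an increase in frequency and/or intensity of the condition". The exacerbation is then itself the event, and it starts after dosing.
- A reader might cite the liver-test rises in protocol 2.3.1, which took 1-2 weeks to normalise, as events likely to be open at the second dose. The same section places them 4-10 weeks into daily dosing and contrasts that with the two single doses here.

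**Conclusion.** The point holds as a gap in a stated rule. Period, and so dose, is assigned by onset only; Period 1 has no upper bound; and nothing says how an event that worsens after the second dose is graded or attributed. If such an event stays one record, the by-period summary does not show the worsening under 60 mg.

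A reader might go further and infer that these events are always counted at their worst grade against 15 mg. The documents neither require nor exclude that. The instruction to update the original CRF leans towards a single record, but it says nothing about start dates or grades, and severity changes are expressly deferred to the guidelines.

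The size is 8.3 points per affected subject in a cohort of 12, or 10.0 in a cohort of 10, taking all subjects in the cohort as dosed in both periods. The number of affected subjects cannot be estimated from the documents. The 67% and 39% in protocol 2.2 are the shares of subjects with any adverse event across three treatments, not the shares with an event still open at a later dose and then worsening. The practical scope is mainly non-laboratory events ongoing at the 60 mg dose.

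**What to change.** In SAP 4.11.1, before database lock:

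1. Define a TEAE as an adverse event that starts, or increases in CTCAE grade, after study drug administration.
2. Run Period 1 from the Period 1 dose up to, but not including, the Period 2 dose, matching SAP 4.10.
3. Count an event whose grade increases after the Period 2 dose as a Period 2 TEAE as well, at the higher grade. Summarise its Period 1 entry at the worst grade reached before that dose.
4. State that TEAE tables are shown by period as well as by cohort and overall.
5. Confirm that the CRF Completion Guidelines either capture the date of each grade change or open a new record. Protocol 10.3.4 requires changes to be documented but does not itself say they are dated, and item 3 cannot be derived without those dates.

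The cost is a few sentences, one derivation and a check of the CRF guidelines, with no new visits or assessments. The one downside is that a single event can appear in both period columns, which a table footnote should explain.

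### The Period 1 TEAE rule in SAP 4.11.1 has no upper bound, so read literally every event after the 60 mg dose falls in both periods

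*SAP*

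**What the plan says.** SAP 4.11.1 (Adverse Events) first states the principle: "TEAEs will further be classified by the Period in which they commenced". It then gives the working rule. A TEAE is "classified as Period 1 if the AE start date/time is on or after the date and time of drug administration in Period 1". The Period 2 condition takes the same form, anchored at the second dose. The Period 1 condition has a start and no end.

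SAP 4.10 (Prior and Concomitant Medications), the section immediately before, opens its period assignment with an equivalent principle but closes the window. Period 1 medications are those starting "on or after the date and time of study drug administration in Period 1 and before study drug administration in Period 2".

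On layout, SAP 4.11.1 describes a TEAE summary that "will be presented for each cohort and overall, by severity and by relationship to study drug", and a second set of tables: "TEAEs and serious TEAEs will be summarized by SOC and Preferred Term for each cohort and overall, and by relationship to study drug". Neither sentence names a period or dose column. SAP 4 (Statistical Analyses) makes a split by cohort and period the default for all analyses, orders the listings by period as well, and lets individual sections depart from that scheme.

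**The concern.** The sentence with the date conditions is the only one in SAP 4.11.1 that gives the periods boundaries, so it is the one that a programmer would turn into code. Everything that happens after the second dose also happens after the first. Taken as written, the Period 1 condition is therefore met by every TEAE with a known start time.

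Every subject receives 15 mg in Period 1 and 60 mg in Period 2, so a period label on a TEAE is a dose label. An output split by period that used the literal rule would show 60 mg events against the 15 mg dose. TEAE incidence is part of the secondary safety endpoint, and the two doses span the range that the trial is meant to support for Japanese patients. A reader would naturally look at tolerability by dose even though no formal comparison is planned.

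**Working it through.** The plan states no figure on this point, so there is none to reproduce. The check applies the two rules to the trial's timeline and then follows the consequence for incidence.

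**Inputs**
- Interval between doses: 14 days, up to 16 (Protocol 4.1).
- Interval from the 60 mg dose to the end-of-study visit: 14 days, up to 16 (Protocol 4.1; SAP 3.2).
- AE collection ends at the end-of-study visit (Protocol 8.3.1).
- Period 1 is 15 mg and Period 2 is 60 mg for every subject (SAP 3.1).

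**Windows.** Let *t* be the AE start time, *d1* the Period 1 dose and *d2* the Period 2 dose.

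| Rule | Period 1 condition | Period 1 window | Share of Period 2 start times also in Period 1 |
|---|---|---|---|
| SAP 4.11.1, literal | *t* ≥ *d1* | 14 + 14 = 28 days; at most 16 + 16 = 32 | 100% |
| Bounded as in SAP 4.10 | *d1* ≤ *t* < *d2* | 14 days; at most 16 | 0% |

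The Period 2 condition, *t* ≥ *d2*, is the same in both rows. Under the bounded rule no known start time after the first dose is left without a period.

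**Consequence for incidence.** Let A be the set of subjects with a TEAE between the doses, B the set with a TEAE after the 60 mg dose, and *n* the number of subjects, taken as the same in both periods.

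- Intended: Period 1 = |A|/*n*; Period 2 = |B|/*n*.
- Literal: Period 1 = |A ∪ B|/*n*; Period 2 = |B|/*n*.
- Because A ∪ B contains B, literal Period 1 incidence is always at least as high as Period 2 incidence.
- The literal difference, Period 2 minus Period 1, is −|A not in B|/*n*. It is zero or negative whatever the true difference is.

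**Illustration with assumed counts** (the documents supply none). Take *n* = 12 in one cohort, |A| = 2 and |B| = 5.

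- Intended: 2/12 = 17% at 15 mg and 5/12 = 42% at 60 mg, a difference of +3/12 = +25 percentage points.
- Literal, if both subjects in A are also in B: |A ∪ B| = 5, so 5/12 = 42% against 42%, a difference of 0. The increase is masked.
- Literal, if no subject is in both sets: |A ∪ B| = 2 + 5 = 7, so 7/12 = 58% against 42%, a difference of −2/12 = −17 points. The increase is reversed.

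The tables by cohort and overall count every TEAE whatever its period, so they are the same under either rule.

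**The case against.** The strongest reply is that the paragraph corrects itself. Its governing sentence places each TEAE in the period in which it began, and an event after the 60 mg dose began in Period 2. Read together, the two sentences give one period per event, and a careful programmer would probably follow that intent. This has force, but it does not remove the defect. SAP 4.10 has an equivalent governing sentence and still writes the upper bound, so the SAP itself treats the bound as part of the definition. Nothing suggests that its absence from 4.11.1 is deliberate.

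The second reply is that 4.11.1 names no period column, while the laboratory and ECG sections (4.11.2 and 4.11.3) do name period. Protocol 9.4.2 also describes the AE tables by cohort and overall. This stands as a limit on the consequence. A reader might infer that 60 mg events will be counted in a 15 mg column; the documents do not establish that. It would need both an AE output split by period and literal programming. Such an output is plausible: it is the SAP 4 default, Protocol 9.4 allows summaries by dose level where appropriate, and the period classification would otherwise have little use. The table shells, which would settle the matter, are not among the documents.

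A reader might also infer that the secondary endpoint as a whole is compromised. It is not. The stated safety objective concerns Japanese and non-Japanese subjects, the cohort and overall tables serve it, and no inferential safety analysis is planned.

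Finally, the error would be easy to spot. Under the literal rule the Period 1 figures would reproduce the all-TEAE figures for known start times, and all AEs are listed.

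**Conclusion.** The point holds as a drafting error in a stated rule. SAP 4.11.1 defines Period 1 by a lower bound only, so every TEAE starting at or after the 60 mg dose meets both definitions. That contradicts both its own governing sentence and the bounded rule in SAP 4.10. The literal Period 1 window is twice the intended one: 28 to 32 days against 14 to 16.

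The effect on results is conditional. Tables by cohort and overall do not change. A TEAE summary or listing split by period would be wrong only if the rule were coded as written. In that case the error has a fixed direction: with the same subjects in both periods, 15 mg incidence cannot fall below 60 mg incidence. It would be tempting to call this a bias toward no difference, but the algebra does not support that, because a true increase with dose can be reversed as well as hidden. If some subjects miss Period 2, the denominators differ and the inequality holds for numbers of subjects with events, not necessarily for percentages.

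The size cannot be estimated, since the documents give no TEAE counts for this trial; the percentages above rest on assumed counts. The point is minor in weight but worth correcting before the outputs are programmed.

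**What to change.** In SAP 4.11.1, end the Period 1 condition at the second dose with the wording that SAP 4.10 already uses, so that it reads "in Period 1 and before study drug administration in Period 2". Overlap between the periods then falls from 100% of Period 2 start times to none, and no known start time after the first dose is left out. For a subject who never receives the 60 mg dose the bound is not reached, so all of that subject's TEAEs stay in Period 1; the programming should treat the missing second dose time accordingly.

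It would also help for 4.11.1 to say whether TEAE tables are split by period in addition to cohort and overall, since the SAP 4 default and the section's own wording point different ways.

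The cost is one clause and, if adopted, one clarifying sentence in the SAP. No new data and no protocol change are needed, and there is no downside.
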